**Sample size.** The sample size calculations are based upon estimates of clinically meaningful mean differences and standard deviations derived from our studies of obese asthmatics at the University of Vermont (although this is predominantly a Caucasian population compared with the Duke site, we have found that methacholine reactivity variability does not differ by race [or BMI] in prior studies of the ALA-ACRC). The analysis is based upon a repeated measures analysis of variance approach. The primary outcome is the methacholine responsiveness. We assume that after treatment with MitoQ, a 20% fall in FEV1 will be detected using a mean methacholine dose of 4 mg/ml, an improvement over the baseline estimate of 2 mg/ml. It is assumed that those in the control group will show no improvement over baseline. Using a within-person standard deviation of 3.0, and the assumptions indicated above, 17 individuals per group would provide 80% power with a 5% significance level to detect a difference between patients assigned to active treatment versus placebo. We will inflate these numbers to allow for a 10% patient drop-out and plan to recruit 40 participants total. Pre- and post- changes in mean lung function (% predicted) and questionnaire scores will be compared for each group, and across groups as described previously.

**Data quality.** Data Quality will be enforced through a variety of techniques, and in collaboration with [name] in biostatistics at UVM. This includes the preparation of a detailed manual of operations, staff training and certification of key staff in study procedures, design of unambiguous self-documenting data collection forms, double data entry, audit of source documents against the central database, automated intra-form and inter-form data consistency checks, range and validity checks during data entry, and centralized eligibility checks and randomization assignments. We will have an in-person training meeting at the start of this clinical study for the Investigators and Coordinators at Duke and UVM.

Data quality will be reviewed and discussed at monthly conference calls. [name] will meet in person no less than three times a year at the Steering Committee meetings of the American Lung Association-Airways Clinical Research Center network.

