**Drug (s)**

**Not applicable**

*Drug name – generic followed by brand name and common abbreviations. Availability – Source and pharmacology; vial or product sizes and supplier. If a placebo will be used, identify its contents and source. (attach investigational drug brochure)*

**Mitoquinol and placebo** will be supplied by MitoQ Ltd, (based in Auckland, New Zealand).

Name and Product. MitoQ™ (Mitoquinol mesylate) capsules

Active ingredient: Mitoquinol mesylate, inactive ingredients microcrystalline cellulose, tapioca, silica dioxide  
Product will be supplied as 20 mg capsules and matching placebo.

**Methacholine** will be purchased as Provocholine® (methapharm) containing 100 mg in 20 ml vials

*Preparation: Reconstitution instructions; preparation of a sterile product, compounded dosage form; mixing guidelines, including fluid and volume required. Identify who will prepare.*

**MitoQ** Product will be supplied as 20 mg capsules and matching placebo.

**Methacholine** will be reconstituted according to the FDA approved package insert. Dosing of methacholine for this study will be: 0.03125 mg/mL, 0.0625 mg/mL, 0.1250 mg/mL, 0.25 mg/mL, 0.5 mg/mL, 1 mg/mL, 2 mg/mL, 4 mg/mL. Solutions will be prepared using Provocholine® 100mg in 20mL Diluent will be 0.9% Normal Saline.

*Storage and stability – for both intact and mixed products.*

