**Inclusion criteria:**

1. participant reported physician diagnosis of asthma
2. participant reported on regular prescribed controller therapy for at least 3 months
3. positive methacholine challenge (as determined by spirometry PD20 or oscillometry PD50 ≤ 4.0 mg/ml at visit 2)
4. age: ≥18 years
5. BMI ≥ 30 kg/m^2 (at visit 1)
6. poorly controlled asthma defined as one of the following:
  - a. Asthma Control Test Score ≤ 19 (at visit 1), or
  - b. Participant reported use of rescue inhaler on average > 2 uses/week for preceding month, or
  - c. Participant reported nocturnal asthma awakening on average 1 or more times / week in preceding month, or
  - d. Participant reported ED/hospital visit or prednisone course for asthma in past six months
7. ability and willingness to provide informed consent

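### The sample-size inputs (within-person SD 3.0, treated mean 4 mg/ml) do not fit a methacholine challenge that ends at 4 mg/mL, and they do not give the stated 80% power

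*Combined protocol and SAP*

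**What the plan says.** The Sample size paragraph (Statistical Considerations) names methacholine responsiveness as the primary outcome and bases the calculation on repeated measures analysis of variance. Its inputs are:

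- Treated mean: a 20% fall in FEV1 "will be detected using a mean methacholine dose of 4 mg/ml", described as "an improvement over the baseline estimate of 2 mg/ml".
- Placebo: "It is assumed that those in the control group will show no improvement over baseline". The between-arm difference is therefore 4 − 2 = 2 mg/ml.
- SD and result: "Using a within-person standard deviation of 3.0, and the assumptions indicated above, 17 individuals per group would provide 80% power with a 5% significance level".
- Source: "standard deviations derived from our studies of obese asthmatics at the University of Vermont".

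The SD carries no units, and no log scale or pre-post correlation is given. Allowing for 10% drop-out, the plan recruits 40.

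Two other places fix the scale of measurement. Under Drug and Device Information, the methacholine concentrations are "0.03125 mg/mL, 0.0625 mg/mL, 0.1250 mg/mL, 0.25 mg/mL, 0.5 mg/mL, 1 mg/mL, 2 mg/mL, 4 mg/mL". Inclusion criterion 3 requires a "positive methacholine challenge (as determined by spirometry PD 20 or oscillometry PD 50 ≤ 4.0 mg/ml at visit 2". The Primary Outcome section defines the endpoint as a change in airway reactivity.

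**The concern.** The SD is the input that most determines the stated power, and here it is large relative to the range that the test can measure. The whole ladder spans about 4 mg/ml, yet the plan assumes that a single person's readings vary with an SD of 3.0 mg/ml and that treated participants average the top step. The text available gives no rule for scoring a participant whose FEV1 has not fallen 20% at 4 mg/mL, and that rule decides whether the inputs are possible.

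The Study Design section says the trial should inform a decision on a full-scale trial. If the SD and the difference belong to a different scale from the one analysed, readers cannot tell how sensitive the trial was. Re-running the formula with 3.0 would not settle this, because 3.0 itself is undefined.

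**Working it through.** **Inputs.** Difference 2 mg/ml, SD 3.0, 17 per group, 5% significance and 10% drop-out come from the Sample size paragraph. The ladder of 0.03125 to 4 mg/mL comes from Drug and Device Information. Two-sided testing is assumed, as sidedness is not stated.

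**1. Trying to reproduce 17 per group.** Normal formula: n per group = 2(1.960 + 0.842)² × SD²/difference².

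- 3.0 as the SD of the compared value: 2 × 7.849 × 9/4 = 35.3, so 36 per group (37 with the t-test).
- 3.0 as a within-person SD with change compared: change SD = 3.0 × √2 = 4.24, and 2 × 7.849 × 18/4 = 70.6, so 71 per group (72 with the t-test).

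Neither gives 17. Power from the noncentral t-test:

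| Reading of 3.0 | 17 per group | 18 per group |
|---|---|---|
| SD of the compared value | 47% | 49% |
| Within-person, change compared (SD 4.24) | 27% | 28% |

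The SD that returns 80% at 17 per group is 2/0.991 = 2.02.

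Other routes to about 17 need something the plan does not state:

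- The one-sample paired normal formula gives (3.0 × 2.802/2)² = 17.7, but that is a within-arm test, not MitoQ versus placebo.
- If 3.0 is a between-person SD, 17 per group needs a pre-post correlation of about 0.78 (change score) or 0.75 (ANCOVA).
- Reading 3.0 as a variance, with a one-sided test of change, gives 19.

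The drop-out step is sound: 34/0.9 = 37.8, so 40 covers it, and 20 × 0.9 = 18 evaluable per group.

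**2. Can a within-person SD be 3.0 on this ladder?** Two readings that differ by d have SD d/√2. The largest d is 4 − 0.03125 = 3.97, so the SD is at most 3.97/√2 = 2.81 (4/√2 = 2.83 if the lower end is 0). This needs no assumption about the mean, the correlation or how the participant qualified. It does assume that no reading is scored above 4.

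**3. Can a change SD be 3.0 on this ladder?** Each visit's SD is at most 3.97/2 = 1.98. With non-negative pre-post correlation, the change SD is at most 1.98 × √2 = 2.81. Reaching 3.0 needs 2 × 1.98² × (1 − ρ) ≥ 9, that is ρ of about −0.14 or lower, even at the largest possible spread.

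**4. Can the treated mean be 4?** If no value exceeds 4, a mean of 4 requires every value to equal 4.

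**5. Is 3.0 perhaps in doublings?** The ladder spans 7 doublings, so an SD of 3.0 would fit (limit 7/√2 = 4.95). But 2 to 4 mg/ml is one doubling, and power at 17 per group is then 16% (effect size 1/3) or 10% (1/4.24).

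**6. Illustration only.** Assume baseline values are log-normal, truncated at 4, with mean 2 and an underlying log2 SD of 1 to 3. The raw SD is then 0.91 to 1.11 mg/ml. One doubling held at the top step gives a difference of about 1.0 to 1.2 mg/ml, and power on end values at 17 per group runs from 96% down to 72%. No document supplies these parameters; they show only that the result can fall on either side of 80%.

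**The case against.** The strongest reply is that the calculation was never on a scale capped at 4. A treated mean of 4 implies values above 4, so the authors presumably had such values in mind. Once they are allowed, 3.0 is not extreme as a total SD: a log-normal with mean 2 and SD 3.0 has a geometric mean of 1.1 and only 12% of values above 4. The scoring rule may also sit in the manual of operations, which the protocol mentions but which is not among the documents. This stands as far as it goes: the limit of about 2.8 is conditional on scoring without extrapolation. It does not supply the missing rule, and it does not make 17 per group follow from 3.0.

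A reader might go further and infer that 3.0 cannot be an SD of the primary endpoint because entry is capped at 4.0 mg/ml with a baseline mean of 2, which limits the SD to √(2 × 1.97) = 1.98. The documents do not support that:

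- Entry is by spirometry or oscillometry, and at visit 2 only. A participant can enter without an FEV1 response at or below 4.0, and no entry limit applies to the follow-up test.
- The 1.98 applies to a single baseline value. The endpoint is a change, whose SD on the ladder can in principle reach 3.97.
- Values coded or extrapolated above 4 would permit 3.0.

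The opposite inference is also tempting: 1.98 is close to the 2.02 that returns 80%, so the stated power might be about right. That does not follow either. A cap at 4 would not sustain the 2 mg/ml difference unless every treated participant scored 4.

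Finally, this is described as a pilot, and the analysis plan reports a 95% confidence interval, so a null result can still be read from the interval. That limits the damage but does not justify the printed power.

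**Conclusion.** The stated 80% is not supported. With the plan's own difference of 2 mg/ml and SD of 3.0, power at 17 per group is 47% or 27%, depending on what 3.0 denotes (two-sided t-test). Separately, the SD and the treated mean do not fit a challenge ending at 4 mg/mL. Scored on that ladder without extrapolation, a within-person SD is at most about 2.8 mg/ml and a treated mean of 4 needs every treated participant at exactly 4. Both inputs are possible only with values above 4 whose scoring is unstated; the SD alone could also be a mislabelled change SD with negative pre-post correlation.

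The point does not show that 3.0 is impossible for this endpoint, nor what the true power is. Neither 47% nor 27% should be read as the trial's power, since both inherit the undefined SD.

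**What to change.** In the Sample size paragraph:

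- State how a participant without a 20% FEV1 fall at 4 mg/mL is scored, and whether the analysis is in mg/ml or log2 units.
- Replace 3.0 with an SD labelled as single-value or change, taken from the earlier University of Vermont data scored by the same rule and, where those data allow, restricted to participants who would meet inclusion criterion 3.
- Use a between-arm difference that can be attained on that scale.
- Reprint the power at 17 and at 18 evaluable per group, and keep N at 40.
- If the earlier data cannot supply that SD, print power over a stated range of SDs and remove the 80% claim.

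The cost is a re-tabulation, if the earlier data permit it, and a revised paragraph. The documents do not say whether those data include repeat challenges or the same ladder, hence the fallback. No patients or procedures are added, and the printed power may move in either direction.

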**Not applicable**

Questionnaires described above will be administered in a private setting at the Vermont Lung Center.

**Statistical Considerations:** *Delineate the precise outcomes to be measured and analyzed. Describe how these results will be measured and statistically analyzed. Delineate methods used to estimate the required number of subjects. Describe power calculations if the study involves comparisons. Perform this analysis on each of the primary and secondary objectives, if possible.*

**Analysis Plan.** Baseline comparability between the two randomized arms will be compared using demographic and outcome variables obtained at baseline to identify potential group comparison confounders. Primary outcomes assessed at the end of the study will be compared using a two-sample t-test and associated 95% confidence interval or a Kruskal-Wallis rank test and nonparametric confidence interval if distributional assumptions are of concern. This will be followed by a pre-post repeated measures mixed linear model to test for group specific baseline to follow-up differences, while for those measures observed at multiple time points, a linear mixed model incorporating time at discrete levels will be implemented. The previous t-test comparisons and the mixed models will be extended to covariance models using baseline mROS, age, sex, BMI, smoking history, duration of asthma and asthma medications, and a confounder score using all items. The effect of medications will be determined by using dummy variables for each class of medication, and by using the cumulative dose of inhaled corticosteroid and  $\beta$  agonist in the regression model. We will compare the rate of events describing any change in medications (whether an increase or decrease), including addition of new anti-asthma drugs and use of steroid tapers in the treatment and placebo groups. Missing data patterns from any lost to follow-up or incomplete data collection will be examined using standard approaches to assess missing at random or missing completely at random assumptions. If missing data is of concern, specific multiple imputation approaches for missing data will be implemented. Analyses using complete data and imputed data sets will be qualitatively compared and presented jointly.

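### The stated 80% power with 17 per group does not follow from the plan's own inputs: a 2 mg/ml difference with an SD of 3.0 gives 47% or 27%, depending on what the SD measures.

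*Combined protocol and SAP*

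**What the plan says.** All the sizing inputs are in the Sample size paragraph under Statistical Considerations.

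- Outcome: "The primary outcome is the methacholine responsiveness".
- MitoQ arm: a "mean methacholine dose of 4 mg/ml, an improvement over the baseline estimate of 2 mg/ml".
- Placebo arm: "It is assumed that those in the control group will show no improvement over baseline".
- Variability: "Using a within-person standard deviation of 3.0, and the assumptions indicated above".
- Method: "The analysis is based upon a repeated measures analysis of variance approach".
- Claim: "17 individuals per group would provide 80% power with a 5% significance level" "to detect a difference between patients assigned to active treatment versus placebo".

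The 17 per group is then inflated for 10% drop-out, and 40 participants are planned. The Analysis Plan paragraph says that primary outcomes at the end of the study "will be compared using a two-sample t-test and associated 95% confidence interval", with a rank-based alternative, followed by a pre-post mixed model. Allocation is 1:1 (Randomization and blinding). No pre-post correlation, transformation, one-sided level or second SD is given.

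**The concern.** A standardised difference of 2/3.0 = 0.67 is too small for 17 per arm to give 80% power in a two-arm comparison, and the repeated-measures framing makes it smaller if 3.0 is truly a within-person SD. The power statement for the primary outcome therefore appears to be wrong, or to rest on an input that is not disclosed.

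The pilot label does not remove the problem. The Protocol Summary makes improvement in airway reactivity the primary aim, and Study Design says the results will feed into a decision about a larger trial. A reader who believes the trial had 80% power for a doubling of the methacholine dose could take a non-significant result as fair evidence against an effect of that size. On the stated inputs, such a result would be expected 53% to 73% of the time even if the effect were real.

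**Working it through.** **Inputs.** Between-arm difference in change δ = (4 − 2) − 0 = 2 mg/ml; n = 17 per arm; α = 0.05. Two-sided testing is inferred from the planned 95% interval. The stated SD is 3.0.

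**Two readings of 3.0.**
- (a) Generous: 3.0 is the SD of the change, or of the end-of-study value.
- (b) As written: 3.0 is the within-person SD of a single measurement, so the change has SD 3.0 × √2 = 4.243.

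**Trying to reproduce the plan's figure.** The normal-approximation formula for two arms is n per arm = 2 × (1.96 + 0.84)² × (SD/δ)². With unrounded quantiles the squared term is 7.849.
- (a) 2 × 7.849 × (3/2)² = 35.3, so 36 per arm (37 by the t distribution).
- (b) 2 × 7.849 × (4.243/2)² = 70.6, so 71 per arm (72 by t).

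Neither gives 17.

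**Power with 17 per arm.** Noncentral t, df = 32, critical value 2.037, noncentrality = δ / (SD × √(2/17)), where √(2/17) = 0.343.
- (a) 2 / (3 × 0.343) = 1.94: power 47.0%.
- (b) 2 / (4.243 × 0.343) = 1.37: power 26.6%.

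With two time points, the group-by-time test of a repeated-measures ANOVA is the same test as the two-sample test on change scores. Its noncentral F calculation with within-person SD 3.0 also gives 26.6%, so the ANOVA framing does not rescue the figure.

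| | (a) SD 3.0 | (b) SD 4.24 |
|---|---|---|
| Power, 17 per arm | 47.0% | 26.6% |
| Power, 20 per arm (no drop-out) | 53.8% | 30.6% |
| n per arm for 80% | 37 | 72 |
| Difference detectable at 80%, 17 per arm | 2.97 mg/ml | 4.20 mg/ml |
| 95% CI half-width, 17 per arm (2.037 × SD × 0.343) | 2.1 mg/ml | 3.0 mg/ml |

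**Other readings.**
- One-sided 5%: 60.2% (a) or 38.2% (b).
- 3.0 as a within-person variance (change SD √6 = 2.449): 63.6% two-sided, 75.3% one-sided.
- 3.0 as the variance of the change (SD 1.732): 90.4%. This exceeds 80% but does not reproduce it, and it contradicts the text, which calls 3.0 a standard deviation.
- Log2 scale, one doubling with SD 3.0: 15.6%.
- 3.0 as a total SD with pre-post correlation 0.5 or 0.7: 47.0% or 68.2% for change scores, 58.6% or 75.2% for ANCOVA.

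**What the claim would need.** With 17 per arm, 80% power requires δ/SD = 0.991, so a change SD of 2/0.991 = 2.02, or a within-person SD of 2.02/√2 = 1.43. If 3.0 is a total SD, the required correlation is 1 − (2.02/3)²/2 = 0.77 for change scores, or √(1 − (2.02/3)²) = 0.74 for ANCOVA.

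**Possible source of 17.** The one-sample (paired) formula gives 7.849 × (3/2)² = 17.66, which is half the two-arm requirement under (a). It tests change within the MitoQ arm alone.

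**Drop-out.** 17/0.9 = 18.9, so 19 per arm and 38 in total; planning 40 is consistent with this step.

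**The case against.** The arithmetic is not in dispute. The best counter-arguments concern how far it reaches.

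*An unstated correlation.* The paragraph invokes repeated measures, and a pre-post correlation may have been used but not reported. If 3.0 were a total SD, a correlation of about 0.74 to 0.77 would restore 80%. This stands as a limit: 27% to 47% is what the stated inputs give, not proof of the trial's real power. It does not save the statement, because the text calls the SD within-person and gives no correlation.

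*The 27% is not for the first-listed test.* The Analysis Plan begins with end-of-study values, whose SD would be a total SD at follow-up, which is not given. This is fair. Reading (a) covers that test if its SD is 3.0; reading (b) applies to change scores and to the pre-post model.

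*The origin of 17 is conjecture.* This is also fair. The one-sample formula rounds up to 18, its exact t version needs 20, and power at 17 is 73% (78.5% by the normal approximation). The shortfall does not depend on this explanation.

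*Measurement range.* The methacholine series in the Drug and Device section ends at 4 mg/ml, and the inclusion criteria set positivity at or below 4.0 mg/ml. Without extrapolation, values lying between 0 and 4 cannot have an SD above 2.0, and a mean of 4 would put everyone at the top concentration. Participants who qualify by oscillometry could exceed 4 by spirometry, so this is not decisive. It is a good reason to define the scale and the SD first, and not to rest the correction on a detectable difference of 3 to 4 mg/ml.

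*Pilot status.* The plan contains no rule for proceeding based on significance, and it already provides for a confidence interval. That softens the consequence but leaves an explicit 80% claim standing.

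**Conclusion.** The concern holds. From the inputs in the Sample size paragraph, 17 per arm gives 47% power (SD of change 3.0) or 27% (within-person SD 3.0) for a 2 mg/ml difference between MitoQ and placebo, not 80%. Even with all 40 participants retained, power is 54% or 31%. At 17 per arm, the expected 95% interval would extend about 2.1 or 3.0 mg/ml either side of the estimate, wider than the assumed effect itself.

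This rests on two-sided testing at 5%, on analysis in mg/ml, and on 3.0 being a standard deviation of one of the two kinds described. Testing one-sided or using repeated-measures ANOVA does not change the conclusion. A high pre-post correlation with 3.0 as a total SD would, but the plan would have to say so. This should be corrected before the plan is relied on, because it misstates the power for the primary outcome.

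**What to change.** Keep 40 participants and rewrite the Sample size paragraph.

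1. State whether 3.0 is the SD of the change, the within-person SD of one measurement or the total SD, and on what scale, given that the methacholine series ends at 4 mg/ml.
2. If a smaller SD or a pre-post correlation was used, give its value and source and show the calculation.
3. Otherwise replace the 80% claim. Possible wording: *With 17 evaluable participants per arm, a two-sided 5% comparison of MitoQ with placebo has about 47% power for a 2 mg/ml difference if the SD of change is 3.0, and about 27% if 3.0 is the within-person SD. The expected 95% confidence interval is the estimate ± 2.1 or ± 3.0 mg/ml respectively.*
4. Name the analysis that the calculation refers to (end-of-study value, change score or baseline-adjusted), so that it matches the primary test in the Analysis Plan.

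The cost is one paragraph of text and a less favourable power statement, with no extra participants, visits or procedures. Keeping 80% as a design target for 2 mg/ml would instead need about 37 or 72 evaluable participants per arm before drop-out, which is a different trial.
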